## PROMIS Integration Phase II (HUM00149448)

Patient satisfaction with treatment	Patient reported satisfaction with treatment, assessed with the Treatment Satisfaction Questionnaire for Medication 1.4 (TSQM) [25]. (Measures 4 domains, including Effectiveness, Side Effects, Convenience, and one global scale item, Global Satisfaction; each domain score ranges from 0-100, with higher score indicating greater satisfaction).	Up to 2 weeks after baseline appointment
Patient satisfaction with care	Patient reported satisfaction with rheumatology care, assessed with the Leeds Satisfaction with Care Questionnaire (score ranges from 1-5, with higher value indicating greater satisfaction) [26].	Up to 2 weeks after baseline appointment
Percent of participants achieving a clinically meaningful improvement at 3 months in the most bothersome PROMIS domain at baseline	Percent of participants achieving a clinically significant improvement in the most bothersome PROMIS domain T-score in sleep disturbance and physical function domains and actual score on 0-10 scale for pain intensity domain from baseline to 3 month's post-baseline.	3 months post-baseline appointment
Change in PROMIS pain intensity between Arms 1 and 2 among participants for whom pain is the most bothersome domain at baseline	Among those for whom pain is the most bothersome domain at baseline, we will compare the change in PROMIS pain intensity scores in Arm 2 vs. Arm 1.	3 months post-baseline appointment
Change in PROMIS physical function between Arms 1 and 2 among participants for whom physical function is the most bothersome domain at baseline	Among those for whom physical function is the most bothersome domain at baseline, we will compare the change in PROMIS physical function scores in Arm 2 vs. Arm 1.	3 months post-baseline appointment
Change in PROMIS sleep disturbance between Arms 1 and 2 among participants for whom physical function is the most bothersome domain at baseline	Among those for whom sleep disturbance is the most bothersome domain at baseline, we will compare the change in PROMIS sleep disturbance scores in Arm 2 vs. Arm 1.	3 months post-baseline appointment

### 3.3. Study Period

## PROMIS Integration Phase II (HUM00149448)

The study intervention will be active for a period of at least 12 months or until the adequate sample size is recruited.

### 3.4. Study Population

The study will include participation of patients with rheumatic diseases.

1. Patients: New and established patients seeking care at Michigan Medicine rheumatology clinics.
  - a. Eligibility criteria:
    - i. Age  $\geq$  18 years
    - ii. Patients should be able to read and write English
    - iii. Patients should have access to the MyUofMHealth patient portal
    - iv. Patients should have access to the internet to be able to complete the PROMIS PRO measures and study surveys online
  - b. Trial inclusion criteria:
    - i. Patients should have completed PROMIS pain, physical function, and sleep disturbance measures at least one day before their baseline appointment
    - ii. At least one of the PROMIS PRO scores should be in the concerning zone (pain intensity  $\geq$  5 (0-10), physical function  $\leq$  40 (on a T-score), or sleep disturbance  $\geq$  60 (on a T-score)).
2. Providers: Rheumatology HCPs, including clinicians and advanced practice providers at Michigan Medicine
  - a. Eligibility criteria:
    - i. Currently treating rheumatology patients

### 3.5. Recruitment

We will inform HCPs in the Division of Rheumatology about the study and what it will entail for patients who decide to participate. To ensure that non-participating HCPs will not be surprised by patients' questions about interventions in the study, we will also inform the rheumatology HCPs about where they can view PROMIS scores in the EMR and about the information that will be shared with patient participants.

We will approach eligible patients with upcoming appointments scheduled with an initial recruitment email, with follow-up contact via email, phone call, or text. Patients will be able to opt out of further communications regarding this study at any time. We will also approach rheumatology HCPs at University of Michigan clinics interested in participating.

Interested patients and HCPs will be contacted and informed about the details of the study. All interested patients and HCPs will be given an informed consent. Patients will be given the choice to opt in to participating in the qualitative portions of the study if interested.

[figure not shown]
### 3.6. Study Activities

This study will have two components: a controlled trial to assess the impact of integrating PROs into clinical practice, and qualitative interviewing (optional for patients and HCP's) to identify barriers to and facilitators of effective integration. This protocol is for the controlled trial.

## PROMIS Integration Phase II (HUM00149448)

Figure 3 (Study Flowchart) and Figure 4 (Study Schedule of Events) show how the different parts of the study will fit together.

**Figure 3. Study Flowchart**

## PROMIS Integration Phase II (HUM00149448)

**Figure 4. Study Schedule of Events**

	Screening*	Baseline/ enrollment**	3 months after baseline appointment	End of study
For patients:				
Informed consent	X			
Patient background survey	X			
PROMIS questionnaires *** (pain intensity, physical function, and sleep disturbance)	X		X	
Email with PRO scores to patients in Arm 1****		X		
Post-appointment survey		X		
3 month follow-up survey			X	
Patient interview (Optional)				X
For HCPs:				
Informed consent	X			
Email Arm 1 enrolled patient PRO score summaries to HCP1		X		
Post-study interview				X

\*Patients will be in the screening phase from time of consent to first reported concerning PROMIS score.

\*\*Patients are enrolled only after reporting a concerning PROMIS score.

\*\*\*Patients are asked to complete PROMIS questionnaires prior to visits as part of standard of care; only PROMIS scores from patients who opt in for screening will be reviewed for eligibility.

\*\*\*\*Only Arm 1 receives scores

Patients will have up to 2 weeks to complete surveys/questionnaires.

## PROMIS Integration Phase II (HUM00149448)

### 3.6.1. Pre-trial Period

Once consented to the study, patients will be asked to complete PRO questionnaires online (which includes PROMIS pain intensity, physical function, and sleep disturbance) that are integrated in the MiChart before their next rheumatology appointment (within 3 weeks prior to their scheduled appointment), as part of the current standard of care for UM rheumatology patients. To promote completion of the PRO questionnaires, we will send email and/or text reminders to all consented patients.

Patients will be enrolled in the trial the first time that they report a concerning level of symptoms (pain intensity  $\geq 5$ , physical function  $\leq 40$ , or sleep disturbance  $\geq 60$ ). Enrolled patients will be randomized to Arm 1 or Arm 2 in 1:1 fashion. Patients who do not have concerning scores will not be enrolled and excluded from the trial.

### 3.6.2. Controlled Trial

#### 3.6.2.1. Trial Study Design

There will be two arms (1: 1 randomization) of the trial to assess PRO integration into care (Figure 3).

- Arm 1: PRO Integration into Clinical Practice Intervention Group
- Arm 2: Usual Care Control Group

#### 3.6.2.2. Interventions

##### **PRO Integration into Clinical Practice Treatment Group**

For Arm 1, PRO scores will be shared with patients and HCPs via an emailed report card in order to facilitate discussion of the PRO scores during consultation. HCPs will document their discussion and recommendations/referrals using the dot phrase in MiChart (Epic EMR).

##### **Usual Care Control Group**

For Arm 2, patients and HCPs will not receive an emailed PROMIS score report. PROMIS scores, however, will be available in the EMR as usual. This arm will receive *usual care*.

#### 3.6.2.3 Stratification, Randomization, and Blinding/masking

Patients eligible for randomization to Arm 1 or Arm 2 will be first stratified based on their concerning PRO domain.

- If the patient has only one concerning PRO domain:
  - Patients will be placed into one of 3 groups: “Concerning pain”, “Concerning sleep” or “Concerning physical function”
- If the patient has more than one concerning PRO domain:

## PROMIS Integration Phase II (HUM00149448)

- Patient will be asked to complete a single-item survey to rank the PRO domains in order of importance.
- Depending on what domain patients indicate is the most concerning to them, patients will be placed into one of 3 groups: "Concerning pain", "Concerning sleep", or "Concerning physical function".

A permuted block randomization scheme stratified by most concerning PRO domain (pain, sleep, physical function) will be created before enrollment begins. Once a participant has completed the screening and evaluation for inclusion/exclusion criteria, the participant will enter the randomization process. Participants will be randomized to Arm 1 and Arm 2 with equal probability (1:1) in RedCap. At time of randomization, the investigator or study coordinator will use the randomization sheet to obtain the assigned randomization number and intervention assignment. In this study, participants and physicians will know the assigned treatment group.

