## PROMIS Integration Phase II (HUM00149448)

**Table 2. Primary, Secondary, and Exploratory Endpoints**

Assessment	Description	Timeframe
PRIMARY ENDPOINTS		
Percent of appointments at which PROMIS scores are documented in the EMR note by the participating HCP	Documentation in EMR notes will be categorized as either 'yes' or 'no' and identified through EMR data pulls.	Each appointment with the HCP during the trial period
SECONDARY ENDPOINTS		
Percent of appointments at which referrals/recommendations related to PROMIS scores are documented in the EMR note by the participating HCP	Documentation in EMR notes will be either 'yes' or 'no' and identified through EMR data pulls.	Each appointment with the HCP during the trial period
Quality of patient-provider communication	Patient-reported assessment of different aspects of patient-provider communication using the Interpersonal Processes of Care (IPC) Survey (29 items), which measures 7 subscales: hurried communication, elicited concerns/responded, explained results/medications, patient-centered decision making, compassion, discrimination, and disrespectful office staff (score for each subscale ranges from 1-5; a higher score indicates better IPC) [24].	Up to 2 weeks after baseline appointment
Change in score of the most bothersome PROMIS domain from baseline to 3 months	Change in the T-score of the most bothersome PROMIS domain at baseline for sleep disturbance and physical function domains, and change in actual score on a scale 0-10 for pain intensity domain.	3 months post-baseline appointment
EXPLORATORY ENDPOINTS		
Percent of participants reporting discussion of PROs with their rheumatology provider during appointments	Patient report of whether or not PROs were discussed during appointment (assessed via survey).	Up to 2 weeks after baseline appointment

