## PROMIS Integration Phase II (HUM00149448)

**Table 3. Study Measures/outcome Variables**

Measure/variable name	Description	Type
PROMIS Numeric Rating Scale v1.0 – Pain Intensity 1a	Patient reported rating of average pain intensity over the last 7 days (instrument, 1 item)	Continuous. Ranges from 0 (no pain) to 10 (worst pain you can think of)
PROMIS Physical Function Computer Adaptive Test (CAT)	Patient reported ability to do activities of daily living (computer adaptive test instrument)	Continuous. T-score ranges from approximately 20 (extreme impairment)-80 (no impairment)
PROMIS Sleep Disturbance CAT	Patient reported sleep quality (computer adaptive test instrument)	Continuous. T-score ranges from approximately 20 (no problems with sleep)-80 (severe problems with sleep)
Interpersonal Processes of Care Survey	Patient reported quality of patient-provider communication (instrument, 29 items) [24]	Continuous scores for 7 domains: hurried communication, elicited concerns/responded, explained results/medications, patient-centered decision making, compassion, discrimination, and disrespectful office staff. Scores range from 1-5 for each domain.
Discussion of PRO scores with patient during the appointment	Patient report of whether the physician discussed the PRO scores during the appointment (post-appointment survey question).	Binary
Satisfaction with rheumatology care	Leeds Satisfaction with Care Questionnaire (post-appointment survey) [26]	Continuous. Score ranges from 1-5, with higher value indicating greater satisfaction.
Satisfaction with treatment	Treatment Satisfaction Questionnaire for Medication 1.4 (post-appointment survey) [25]	Continuous. Measures 4 domains, including Effectiveness, Side Effects, Convenience, and one global scale item, Global Satisfaction; each domain score ranges from 0-100, with higher score indicating greater satisfaction.
Documentation of PRO scores in the EMR note	Whether the HCP imported the PRO scores into the EMR note (outcome)	Binary

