## PROMIS Integration Phase II (HUM00149448)

Interpretation of PRO scores	Whether the HCP interpreted the PRO scores (outcome)	Binary
Clinical decision	What decision was taken at the appointment to address the patient's issues (outcome).	Categorical. Possible decisions include: medication change, referral to another provider, and no action taken.

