### 3.7. Study Analyses

Our data sources for this study will be electronic medical records (EMR), survey responses collected through REDCap, and qualitative data collected through semi-structured interviews. We will utilize the Data Direct tool to assist with exporting quantitative data from the EMR, and the EMERSE tool to assist with reviewing textual data from the EMR (<https://research.medicine.umich.edu/our-units/data-office-clinical-translational-research/data-access/self-serve-data-tools>).

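### Nothing masks whoever codes the EMR notes, although two outcomes (score-related referrals or recommendations, and interpretation of scores) need judgement; withholding the arm during coding is a cheap improvement

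*Combined protocol and SAP*

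**What the plan says.** **Masking.** Section 3.6.2.3 is the section headed for masking. Its only statement on the subject is "In this study, participants and physicians will know the assigned treatment group". The same section says that "the investigator or study coordinator will use the randomization sheet to obtain the assigned randomization number and intervention assignment", so at least some study staff know the arm.

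**Outcomes that rest on the notes.** The first secondary endpoint in Table 2 is "Percent of appointments at which referrals/recommendations related to PROMIS scores are documented in the EMR note by the participating HCP". Table 2 describes how it is obtained: "Documentation in EMR notes will be either 'yes' or 'no' and identified through EMR data pulls". Table 3 adds a second binary outcome, "Whether the HCP interpreted the PRO scores (outcome". Sections 3.6.2.4 and 3.7 say that the study will use "the EMERSE tool to assist with reviewing textual data from the EMR".

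**What is not there.** The plan does not say who codes these outcomes, by what rule, or whether that person knows the arm. The de-identification and inter-rater checks in section 3.7.2 apply to interview transcripts and free-text survey comments, not to EMR notes.

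**The concern.** A data pull can show that a referral exists. It cannot show that the referral was made because of a PROMIS score. Every randomized patient has at least one concerning score (section 3.4), so many ordinary rheumatology actions could plausibly be called related to it. Whether a sentence in a note amounts to interpreting a score is a similar call.

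A coder who knows that a patient received the report card may resolve doubtful cases toward yes in Arm 1 and toward no in Arm 2. Such a bias does not shrink as patients are added. Section 3.7.1 justifies the sample by the point estimates it will give for a Phase 3 trial, so an inflated referral difference would carry into the design of that trial.

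**Working it through.** The plan gives no figure to reproduce here. Section 3.7.1 calls the 300 a convenience sample and states no rates, effect size or power. The check has two parts.

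**1. Which outcomes are exposed**

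| Outcome | Source in the plan | Judgement needed? |
|---|---|---|
| Scores documented (primary) | Table 2, data pull; Table 3, import into the note | Little: import is close to a present/absent check |
| Score-related referral or recommendation (secondary) | Table 2, data pull; text review in 3.6.2.4 and 3.7 | Yes: the reason for the action must be inferred; no rule given |
| Interpretation of scores | Table 3; text review | Yes: no rule given |
| Clinical decision | Table 3; 3.6.2.4 lists medication changes and referrals as EMR data | Could come largely from structured fields |

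**2. How large a tilt could be (assumed inputs)**

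From the plan: up to 300 patients randomized 1:1, so 150 per arm, and a significance level of 0.05 (two-sided assumed). Also assumed: one independent appointment per patient, no true difference, and the rates shown below.

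*Precision.* The 95% CI half-width for a difference at a common rate p is 1.96 × √(2p(1−p)/150).
- p = 20%: 1.96 × √(0.32/150) = 9.1 points
- p = 30%: 1.96 × √(0.42/150) = 10.4 points
- p = 50%: 1.96 × √(0.50/150) = 11.3 points

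*Borderline notes.* The false difference is (share borderline) × (yes-rate among these in Arm 1 − yes-rate in Arm 2).
- 20% borderline, 60% vs 40%: 0.20 × 0.20 = 4 points
- 10% borderline, same split: 0.10 × 0.20 = 2 points
- 30% borderline, same split: 0.30 × 0.20 = 6 points
- 20% borderline, 75% vs 25% (an extreme split): 0.20 × 0.50 = 10 points

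The 4-point case is between 4/11.3 = 35% and 4/9.1 = 44% of the half-width.

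*False-positive rate.* Suppose instead that a fraction f of true-no Arm 1 notes is coded yes. The shift is d = (1−p)f. The rejection rate of the pooled two-proportion test is Φ((d − 1.96·SE₀)/SE₁) + Φ((−d − 1.96·SE₀)/SE₁). For p = 20% and f = 5%: d = 0.04, SE₀ = √(2 × 0.22 × 0.78/150) = 0.0478, SE₁ = √((0.24 × 0.76 + 0.20 × 0.80)/150) = 0.0478. The result is 0.130 + 0.003 = 13%.

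| True rate p | f = 0 | f = 5% | f = 10% | f = 15% |
|---|---|---|---|---|
| 20% | 5% | 13% | 37% | 66% |
| 30% | 5% | 10% | 25% | 48% |
| 50% | 5% | 7% | 14% | 26% |

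The f = 0 column is the case where coding errors do not differ between arms, which is what masking aims at.

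**The case against.** **The plan is silent rather than wrong.** A reader might infer that it provides for unmasked coding, or that the staff who handle assignments also code the notes. The documents support neither. They do not say who reviews notes, who emails the cards, or how large the team is. What stands is that nothing separates knowledge of the arm from coding.

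**The primary endpoint.** A reader might also infer that the primary result is biased. Table 3 defines that measure as "Whether the HCP imported the PRO scores into the EMR note (outcome", and section 2.1 describes import by dot phrase. That leaves little room for opinion. Table 2 speaks of documentation rather than import, so a typed or paraphrased score could still need a call, but this is a small residue. The 4-point illustration should not be applied to the primary endpoint.

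**Masking may fail.** In Arm 1, "HCPs will document their discussion and recommendations/referrals using the dot phrase in MiChart (Epic EMR", and some notes may mention the emailed card. This stands in part. However, section 3.6.2.2 keeps the scores available in the EMR for Arm 2. In Phase I, HCPs trained to import scores did so in 2,745 of 3,969 encounters with completed questionnaires (69.2%), before any report card. A dot phrase in the note therefore does not identify the arm with certainty, and withholding the arm field still removes real information.

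**Open-label treatment.** Unmasked patients and physicians are not the defect. An intervention that consists of a report sent to both cannot be hidden from them.

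**The size is assumed.** This stands. Every coding rate above is hypothetical, and Table 2 counts appointments, so 150 per arm need not be the denominator.

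**Conclusion.** The concern holds for two outcomes: the secondary referral/recommendation endpoint and the interpretation measure. Both need a reading of note text, neither has a rule, and the plan does not keep the arm from whoever does the reading.

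Under the assumed 20% borderline notes and a 60% vs 40% split, the false difference is 4 points against a half-width of about 9 to 11 points. That is not negligible for a pilot whose purpose is estimation, but it is an illustration and not an estimate of bias in this trial. No figure in the plan is contradicted.

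It would go too far to call the remedy free. The handling takes some work, and the masking will be incomplete. This is a cheap improvement.

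**What to change.** In sections 3.6.2.3 and 3.6.2.4, for these two outcomes:

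1. State who codes the notes; existing staff suffice.
2. Give a written yes/no rule for when a referral or recommendation counts as related to the scores, and for when a score counts as interpreted.
3. Export notes by study ID without the arm field, and mix them across arms before coding.
4. Lock the codes before they are linked to the REDCap allocation.
5. Have coders record when a note reveals the arm, and report how often this happened.

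References to the emailed card should not be deleted from the notes. Only Arm 1 patients and their HCPs receive the card, so deletion would alter text in one arm only. It could also remove the evidence that a recommendation was score-related, which would itself bias the coding.

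The cost is a little more data handling and the time to write the rule. It needs no added patients, visits or data. Some notes will still reveal the arm.

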### 3.6.2.4. Outcome Assessment

Health outcomes (PROMIS pain intensity, physical function and sleep disturbance) will be assessed before appointments and at three (3) months post appointment with an online patient-reported survey.

Patient-provider communication, the patient's experience with the PRO scores, and satisfaction with disease management will be assessed with a patient-reported survey after the appointment.

Process of care measures (documentation and interpretation of PRO scores, clinical decisions) will be assessed for each appointment using data from the EMR (notes, medication changes, and referrals). We will utilize the Data Direct tool to assist with exporting quantitative data from the EMR, and the EMERSE tool to assist with reviewing textual data from the EMR (<https://research.medicine.umich.edu/our-units/data-office-clinical-translational-research/data-access/self-serve-data-tools>).

### Study Measures/outcome Variables

Table 3 below summarizes the measures and outcomes to be used to compare health outcomes and processes of care for the different study arms.

Patient-provider communication will be measured using the Interpersonal Process of Care Survey (IPCS) with a 12-item communication subscale and an 8-item patient-centered decision making subscale [24]. It has been used to predict patient satisfaction [30].

Satisfaction with treatment will be measured using the Treatment Satisfaction Questionnaire for Medication (TSQM version 1.4) [25].

Satisfaction with care will be measured using the Leeds Satisfaction with Care Questionnaire, which was developed for patients to assess quality of rheumatology care [26].

